7.2 Statistical Analyses

Data analysis from this multi-center clinical trial will be performed to characterize 2D and 4D CEUS as a follow-up imaging tool for the evaluation of residual tumoral blood flow in patients with HCC treated with TACE.

Our statistical analysis will address three major questions:

1. Does 2D and 4D CEUS 1-2 weeks post TACE yield sensitivity and specificity greater than 90% for identifying residual tumor blood flow, thereby providing reliable earlier identification (relative to the current clinical standard) of patients in need of retreatment?
2. Does 2D and 4D CEUS 1 month post TACE yield sensitivity and specificity greater than 90% for identifying residual tumor blood flow, thereby providing an accurate, safe, and cost-effective imaging alternative for identifying TACE patients in need of retreatment?
3. Are quantifiable biomarkers generated by parametric imaging of 2D and 4D CEUS exams able to differentiate between fully treated and incompletely treated masses by measuring blood flow kinetics?

The first three cases at each institution will be used as reader training cases and will not be included in the final analysis. In the event of all cases showing identical response (i.e. all incompletely or completely treated), the first case with an alternative outcome will be substituted for the 9th case. Following reader training, each reader (all of whom have previous experience with CEUS and volumetric ultrasound) will be asked to evaluate all 201 remaining cases. 2D and 4D CEUS exams will be read separately and only after randomization. 2D cases will be viewed in a standard DICOM viewer, while 4D cases will be viewed in GE's 4D View software. Readers will first be asked to review both the patient's baseline CE-MRI/CT and CEUS exams to identify the size and location of the treated mass. Following baseline review, each reader will review the 1-2 week and 1 month CEUS exam (in random order). Intratumoral blood flow will be assessed as present or not present. Readers will then be asked to interpret the patient's 1 month follow-up CE-MRI/CT images and again evaluate the need to retreat based on residual blood flow. Finally, when available, readers will review subsequent CE-MRI/CT imaging studies (up to six months post TACE). MRI/CT evaluations will be based on mRECIST criteria. All imaging studies will be read twice by each

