reader. Studies will be presented in random order. The second round reads will be performed at least one month after the first. Outcomes will be defined as incompletely treated (i.e. requiring retreatment) based on (in order of preference of reference standard): a) pathological examination of explanted livers demonstrating live tumors; b) tumor enhancement seen with CT or MR and confirmed via angiography during retreatment; c) tumor growth on 6 month follow-up CE-CT/MRI; or d) asymmetrical or nodular tumor enhancement on CE-MRI/CT on 6 month follow-up. Incomplete treatment on CEUS (2D or 4D) will be evaluated by each reader and evidenced by the tumor showing either residual blood flow after treatment or nodular peripheral blood flow.

For questions 1-2, sensitivity (the ability to detect patients in need of retreatment) and specificity (the ability to identify patients who do not require retreatment) will first be calculated on a reader by reader basis. Four 2 x 2 tables will be constructed comparing the need for re-treatment based on the clinical gold standard described above and CEUS, tabulating true positives, false positives, false negatives, and true negatives. A table will be created for CEUS at 1-2 weeks and 1 month for both 2D and 4D CEUS and used to calculate sensitivity, specificity, accuracy, positive predictive value, and negative predictive value. Statistical significance between the reference standard and each of the 4 CEUS groups will be determined using a McNemar test. These values will also be calculated based on the majority decision (i.e. 4 or more readers in agreement). In the event of discordant readings during this analysis, tumor outcome will be decided by consensus by the two readers at TJU. Differences between techniques (2D vs. 4D) and time points (1-2 weeks vs. 1 month post treatment) will be determined by comparing areas under the receiver operating characteristic curves for each modality/time point based on necessity of tumor retreatment. Intra-rater and inter-rater variability will be calculated using a Shrout and Fleiss Interclass Correlation [Shrout and Fleiss 1979]. Finally, a logistical regression and analysis of variance will be performed to determine if significant variations exist between individual sites (to determine operator dependence), lesion size (tumor size dependency) or between patients treated with cTACE vs. DEB-TACE (treatment dependency).

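### The only 6-month MRI/CT read the plan describes is made unmasked by the CEUS readers after CEUS, so reference tiers c and d are not protected from the CEUS call

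*Combined protocol and SAP*

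**What the plan says.** Section 7.2 fixes the order of reading within a patient; section 6.5 and the synopsis repeat it. After baseline imaging, "Following baseline review, each reader will review the 1-2 week and 1 month CEUS exam (in random order"). Next, "Readers will then be asked to interpret the patient's 1 month follow-up CE-MRI/CT images", judging the need for retreatment a second time. Last, "Finally, when available, readers will review subsequent CE-MRI/CT imaging studies (up to six months post TACE").

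The reference standard is a ranked list:

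- Tier a: "a) pathological examination of explanted livers demonstrating live tumors".
- Tier b: "b) tumor enhancement seen with CT or MR and confirmed via angiography during retreatment".
- Tiers c and d: "c) tumor growth on 6 month follow-up CE-CT/MRI; or d) asymmetrical or nodular tumor enhancement on CE-MRI/CT on 6 month follow-up".

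In the majority-decision analysis, discordant readings go to two of the same readers: "tumor outcome will be decided by consensus by the two readers at TJU". Every study is read twice, and "The second round reads will be performed at least one month after the first". Section 5.4 deals with blinding to the drug only. No section says that whoever reads MRI/CT is masked to CEUS, and none names who assigns tiers c and d.

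**The concern.** Sensitivity and specificity against the reference are the primary objective, each to be shown above 90%. That needs a reference decided without knowledge of the test. Under the stated sequence, the person looking at 6-month enhancement has already recorded a CEUS call on the same lesion. A reader who called it CEUS-negative may discount faint enhancement. One who called it CEUS-positive may credit it. Either way a discordant case becomes concordant, and apparent accuracy rises.

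Locking the CEUS call before MRI/CT is opened would not help, because that protects the test and not the reference. The influence also cannot be removed by analysis once the reads are done.

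Specificity is the more exposed measure. Tier b needs retreatment, so it labels only positives. Without an explant, a lesion can be called completely treated only because follow-up imaging was negative. Specificity also has the smaller planned margin: 85% power, against 99% for sensitivity.

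**Working it through.** **1. The plan's own figures (section 7.2.1).** Inputs: null 0.90, alternative 0.98, alpha 0.05, and the table row for N = 200 with 133 diseased and therefore 200 - 133 = 67 not diseased. The exact binomial test rejects when the number correct is at least r, where r is the smallest count with P(X >= r | n, 0.90) <= alpha.

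- Sensitivity: n = 133, r = 126, actual alpha 0.0385, power 0.9945.
- Specificity: n = 67, r = 65, actual alpha 0.0307, power 0.8494.

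Both match the printed row at one-sided 0.05. At one-sided 0.025 specificity power would be 0.612, so the plan's calculation is one-sided 0.05. These figures presume a reference that does not depend on CEUS.

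**2. Effect on specificity.** Assume true specificity is exactly 0.90. Let e be the share of negatives labelled from tiers c/d, and s the share of exposed CEUS false positives that the influenced read turns into reference-positives. Then:

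- share of negatives remaining = 0.90 + 0.10 x (1 - e x s)
- apparent specificity = 0.90 / share remaining
- negatives remaining = 67 x share remaining, rounded

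The plan applies a Bonferroni-type adjustment but does not state the number of tests. The last column assumes four CEUS groups: 0.05 / 4 = 0.0125.

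| e | s | Share remaining | Apparent specificity | n | False success, 0.05 (r) | False success, 0.0125 (r) |
|---|---|---|---|---|---|---|
| any | 0 | 1.00 | 90.0% | 67 | 3.1% (65) | 0.7% (66) |
| 1 | 0.20 | 0.98 | 91.8% | 66 | 8.6% (64) | 2.5% (65) |
| 1 | 0.50 | 0.95 | 94.7% | 64 | 33.9% (62) | 14.3% (63) |
| 0.5 | 0.20 | 0.99 | 90.9% | 66 | 5.4% (64) | 1.4% (65) |
| 0.25 | 0.20 | 0.995 | 90.5% | 67 | 3.9% (65) | 1.0% (66) |

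**3. Both discordant cells moved.** Let f be the share of all patients labelled from c/d, and w the share of their CEUS-discordant reference reads pulled to agree with CEUS; k = f x w. With prevalence 0.667 and both true values 0.90, the cells are TP 0.6003, FN 0.0667, FP 0.0333 and TN 0.2997. A fraction k of FN moves to TN, and k of FP moves to TP. For f = 0.5 and w = 0.25, k = 0.125:

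- sensitivity = (0.6003 + 0.125 x 0.0333) / (0.6003 + 0.125 x 0.0333 + 0.875 x 0.0667) = 91.2%
- specificity = (0.2997 + 0.125 x 0.0667) / (0.2997 + 0.125 x 0.0667 + 0.875 x 0.0333) = 91.4%

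Holding n at 133 and 67 and testing at one-sided 0.05, the false-success chances are 9.3% (sensitivity) and 6.4% (specificity). The range runs from 4.6% and 3.6% (f = 0.25, w = 0.10) to 62.6% and 37.6% (f = 1, w = 0.5). With w = 0 there is no inflation.

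In this model, which exposes positives and negatives equally, the sensitivity test is affected at least as much. The view that specificity suffers most therefore rests on tiers a and b shielding positives, and not on the arithmetic of the tests.

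**The case against.** The strongest reply is that no section says these reads set tiers c and d. Only the CEUS call is expressly given to each reader. The 2 x 2 tables refer to a clinical gold standard, and 1-month follow-up imaging is part of routine care, so the label could come from clinical reports. This stands as a limit on the claim. It does not secure independence, because the readers' review is the only 6-month read described, and discordant outcomes also go to readers.

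Other points stand in part:

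- MRI/CT is to be judged by mRECIST, and growth (tier c) is less open to suggestion than nodular or asymmetrical enhancement (tier d).
- Pathology, and largely angiographic confirmation, lie outside the readers' influence and take precedence.
- The 1-month MRI/CT read comes between CEUS and the 6-month read and may itself be the stronger anchor. It would be wrong to say that the 6-month images are read immediately after CEUS.

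A reader might infer two stronger things. One is that each reader carries a personal reference label. The plan's reader-by-reader wording describes how accuracy is calculated and does not establish that. The other is that accuracy is inflated as a matter of fact. The documents support an expected direction only.

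Two possible defences fail. Random presentation order does not mask a reader to a call made earlier in a fixed sequence. De-identified images do not hide the reader's own CEUS result.

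**Conclusion.** The concern holds in a conditional form. Followed as written, the plan does not protect tiers c and d from the CEUS call wherever the readers' own 6-month review supplies the label. The expected bias favours CEUS, mainly in specificity.

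Its size cannot be fixed from the documents, which give neither the share of labels resting on c/d nor any relabelling rate. The upper figures (about 9-34% at 0.05, about 2.5-14% at 0.0125) assume that every negative rests on c/d and that 20-50% of CEUS false positives are relabelled. With half the negatives exposed and 20% relabelled, the rate at 0.05 is about 5.4%, a modest rise from 3.1%. At the assumed adjusted level, the 20% case stays below 5% even with full exposure. The point should be settled before reading starts.

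**What to change.** In sections 6.5 and 7.2, and in the synopsis, do one of the following:

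1. Take follow-up CE-MRI/CT out of the CEUS reading sequence. Have the same readers read it in a separate session, de-identified and in random order, without CEUS images or CEUS calls. State a new minimum interval from the CEUS reads; the existing one-month gap separates the first and second read rounds, not CEUS from MRI/CT.
2. Set tiers c and d from the standard-of-care radiology report, and state that it is made without CEUS results. If this is already the intent, a sentence saying so is enough.

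Under either option, name who assigns the reference and state that one reference label per lesion is used for all readers.

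The cost is protocol wording and, under option 1, additional MRI/CT sessions in each read round for every reader. No extra readers, scans or patients are needed, and sample size and planned power (0.9945 and 0.8494) do not change.

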1. INTRODUCTION

Hepatocellular carcinoma (HCC) is the third leading cause of cancer mortality worldwide and the incidence is increasing. While surgical resection and transplantation offer the possibility of long-term cure, the majority of patients are not eligible for these treatments. Transarterial chemoembolization (TACE) is standard of care for patients with Barcelona Clinic Liver Cancer stage B disease but may also be used as bridging therapy in patients who are potential transplant candidates. Current guidelines recommend follow-up imaging 4-6 weeks after all tumor-bearing areas have been treated. Incomplete treatment is defined as persistence of enhancing areas inside the treated lesions seen at the first imaging study after locoregional treatment and is observed in up to two-thirds of patients post TACE. Contrast-enhanced magnetic resonance imaging (CE-MRI) has been established as the clinical standard imaging modality for evaluating treatment

response and contrast-enhanced computed tomography (CE-CT) is used when CE-MRI is contraindicated. However, there are multiple reasons patients may not undergo cross-sectional imaging follow-up - metallic implants, renal impairment, allergies to contrast medium, and anxieties related to confined space or radiation exposure. Additionally, the cost and availability of these techniques are disadvantageous compared to ultrasound imaging.

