While follow-up imaging standards are well established, several limitations exist. CE-MRI may not be feasible in patients with metallic implants, renal contraindications (glomerular filtration rates <30 mL/min/1.73 m² [Shellock and Spinazzi 2008]), the inability to breath hold or claustrophobia. CECT may be contraindicated in patients with severe allergy to iodinated contrast and renal impairment. The radiation exposure associated with repeated CT imaging (particularly in patients who undergo multiple TACE treatments) also renders CT a suboptimal imaging modality. Additionally, the costs and limited availability

of CE-MRI or CT may place a significant, unnecessary burden on the health system. A final limitation of existing imaging techniques is the required delay between treatment and imaging to evaluate response due to the inherent properties of the MRI/CT contrast media and the presence of Lipiodol in the background liver. Consequently, time to retreatment is prolonged and in patients where TACE is used to downstage disease, a decision regarding transplantation is delayed. Phase II efficacy and pharmacokinetic studies show liver function generally returns to normal within 7 days after DEB-TACE [Varela et al. 2007]; thus, retreatment before the standard 5-7 weeks is feasible. In addition, retreatment by ablation may also be performed earlier with advanced screening of effective embolization. An imaging test that provides earlier identification of tumoral blood flow after TACE would shorten the time between treatments and potentially improve patient outcomes. Once tumor avascularity is confirmed, patients could resume standardized CE-MRI/CT long term follow-up protocols.

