3.1 Trial Duration

Individual participation in this trial will be limited to three ultrasound imaging studies. Exams will take place the morning prior to treatment, one to two weeks post embolization, and prior to the patient's one month follow-up (scheduled as part of clinical care). If the patient fails to show up for the one week, CEUS exam, they will not be excluded from the final ultrasound exam. The entire ultrasound imaging protocol will require approximately one hour including a 30 min observation period. Patients will be monitored for at least 30 minutes before being escorted to procedure or clinically scheduled imaging.

Subject recruitment is expected to last 5 years (January 2016 – December 2020). Analysis and publication of results are expected to take an additional 2 months (December 2020– January 2021). Volunteer Registry Database forms will be submitted to the National Institute of Health's Office of Regulatory Compliance and Quality at the completion of the research study.

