For statistical question 3, all quantitative parameters will be compared between fully treated and incompletely treated masses using a Student's t-test. Additionally, lesions that demonstrate lack of residual enhancement at 1 month, but show recurrence at 6 month follow-up, will be compared to completely treated masses to determine if quantitative CEUS parameters can detect this lower level of residual disease. Statistical analysis will be performed with assistance from the biostatistician co-investigator using Stata 12.0 (Stata Corp, College Station, TX) with p values < 0.05 considered statistically significant after a Bonferroni-type adjustment for multiple tests. These statistical tests will answer our three major questions regarding the sensitivity and specificity of 2D and 4D CEUS as an imaging tool for the follow-up of TACE

at 1-2 weeks and 1 month (specific aims 1-2), as well as the influence of operator, reader, tumor size, and embolization material.

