0.9791	0.7135	107							
160	0.9000	0.9800	0.9000	0.9800	0.0500	0.0374	0.0259	0.6670	
0.9735	0.6839	113							
170	0.9000	0.9800	0.9000	0.9800	0.0500	0.0255	0.0181	0.6670	
0.9893	0.6619	120							
180	0.9000	0.9800	0.9000	0.9800	0.0500	0.0382	0.0138	0.6670	
0.9857	0.8879	127							
190	0.9000	0.9800	0.9000	0.9800	0.0500	0.0250	0.0421	0.6670	
0.9945	0.8494	133							
200	0.9000	0.9800	0.9000	0.9800	0.0500	0.0385	0.0307	0.6670	

A total of 201 patients will be used in the final analysis for this study (the first 9 will be used as training cases and excluded), of which 135 (66.7%) will require retreatment. A total sample size of 201 (which includes 133 subjects with the disease) achieves 99% power to reject the null hypothesis for sensitivity, and 85% power to reject the null hypothesis for specificity.

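### The reference standard leaves three kinds of lesion without a sound label, and the expected dates in 3.1 cannot supply the 6-month reference for the last 5 to 6 months of accrual

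*Combined protocol and SAP*

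**What the plan says.** The synopsis, 6.5 and 7.2 carry the same rule. It opens "Outcomes will be defined as incompletely treated (i.e. requiring retreatment) based on (in order of preference of reference standard" and then ranks four tiers: (a) live tumour in an explanted liver, then "b) tumor enhancement seen with CT or MR and confirmed via angiography during retreatment; c) tumor growth on 6 month follow-up CE-CT/MRI", and last (d) asymmetrical or nodular enhancement at 6 months. Only the positive class is defined. Completely treated is the complement, a reading that the question 3 analysis in 7.2 partly supports, since there "lesions that demonstrate lack of residual enhancement at 1 month, but show recurrence at 6 month follow-up, will be compared to completely treated masses".

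Later scans are not guaranteed: "Finally, when available, readers will review subsequent CE-MRI/CT imaging studies (up to six months post TACE"). Trial completion in 6.7.1 requires the 1-month MRI but no 6-month scan. The 1-month CE-MRI/CT is read, but no tier makes it a fallback reference.

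On retreatment, section 1.1 expects repeat TACE or other treatments, continued until arterial enhancement has gone. It also notes that "retreatment by ablation may also be performed earlier with advanced screening of effective embolization". Section 1 says TACE "may also be used as bridging therapy in patients who are potential transplant candidates".

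Section 3.1 expects recruitment from January 2016 to December 2020, and then "Analysis and publication of results are expected to take an additional 2 months", ending in January 2021. Section 7.2 has every study read twice by each reader, with at least one month between rounds. Section 7.2.1 states: "A total of 201 patients will be used in the final analysis for this study".

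**The concern.** Sensitivity and specificity are the primary results, and both depend on the reference label. Three cases have no sound label:

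- **Retreated without angiographic confirmation.** Tier (b) is not met. Tiers (c) and (d) then look at a 6-month scan that shows the effect of the retreatment. A clear scan would make the lesion completely treated.
- **Clear explant after retreatment.** Tier (a) ranks first and carries no condition on what happened between the index TACE and the explant. The text does not say whether a clear explant overrides a positive under (b).
- **No explant, no confirmed retreatment and no 6-month scan.** No tier applies, and the plan has no indeterminate or missing category. The consensus rule in 7.2 settles discordant readings, not missing references.

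The errors act in different directions. A residual lesion labelled negative turns a correct positive CEUS into a false positive and lowers specificity. A recurrence that CEUS missed, labelled negative by default, turns a false negative into a true negative and raises sensitivity. With no stated rule, these labels could be settled after the CEUS reads are known.

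The calendar adds to the third case. Tiers (a) and (b) give only positive labels, so a patient who is neither retreated nor transplanted can be judged only at 6 months. Missing 6-month scans therefore fall mainly on the reference-negatives, the smaller group, on which specificity rests.

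**Working it through.** **Inputs.** From 7.2.1: N = 201, prevalence 66.7%, null 90%, alternative 98%, alpha 0.05. Expected negatives: 201 × 0.333 ≈ 67. From 3.1: 60 months of recruitment to December 2020, with publication by January 2021. From 7.2: two read rounds at least one month apart. Even accrual is my assumption. Like 7.2.1, I count one lesion per patient.

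**Step 1: reproduce the plan's power.** Exact one-sided binomial test: take the smallest r with P(X ≥ r | n, 0.90) ≤ 0.05; power is P(X ≥ r | n, 0.98).
- n = 133: r = 126, alpha 0.0385, power 99.4%.
- n = 67: r = 65, alpha 0.0307, power 84.9%.

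These match the plan's 99% and 85%. Both assume that every patient has a label.

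**Step 2: calendar.**
- A 6-month scan that exists by 31 January 2021 needs TACE by about 31 July 2020. August to December is 5 months.
- If that scan must be read twice by then, the first round ends by about 31 December 2020, so TACE is needed by about 30 June 2020. July to December is 6 months.

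| Months lost (m) | Patients, 201 × m/60 | Expected negatives, 67 × m/60 |
|---|---|---|
| 5 | 16.8 | 5.6 |
| 6 | 20.1 | 6.7 |

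**Step 3: specificity power if the late negatives are lost.** The number of negatives is random, so I average the exact power over a binomial count with N = 201 and probability 0.333 × (1 − m/60).

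| m | Averaged power |
|---|---|
| 0 | 82.7% |
| 5 | 78.1% |
| 6 | 77.1% |

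Dropping all late patients instead, positives included, gives the same values to one decimal (N = 184: 78.1%; N = 181: 77.1%). At a fixed n the exact test is uneven: 61 negatives (59 must be correct) gives 87.7%, and 60 negatives (59 must still be correct) gives 66.2%.

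**Step 4: one mislabelled lesion (illustration only).** Add one residual lesion to the 67 true negatives. The test then needs 66 of 68 read as negative. CEUS reads the residual lesion as negative with probability 0.02.
- P(at least 66 of 67 correct) = 0.6115; P(at least 65 of 67) = 0.8494.
- Chance of passing = 0.98 × 0.6115 + 0.02 × 0.8494 = 0.616, against 0.849 with no mislabelling.

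**Step 5: room on the sensitivity side.** The table in 7.2.1 shows sensitivity power of 98.9% with 120 positives and 94.9% with 100. Against about 134 expected positives, leaving out 14 or 34 retreated lesions in a supporting analysis is affordable.

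**The case against.** The ordering does more than a quick reading suggests. A reader might infer that every retreated lesion, or every explant, lacks a rule. The text does not support that. Tier (b) outranks (c) and (d), so retreatment confirmed by angiography is positive whatever the 6-month scan shows, and repeat TACE is itself done under fluoroscopic guidance. A live-tumour explant is positive under (a). The plan also equates incomplete treatment with needing retreatment, so a careful analyst would probably not call a retreated residual lesion completely treated. This narrows the gap to the three cases above. It does not close it, because the listed tiers and that gloss give different answers for those cases.

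The ablation remark in 1.1 describes a possible benefit of earlier imaging, not a forecast for this trial. The more general text there on other treatments is the better support, and neither gives a frequency.

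The dates in 3.1 are expectations and 210 is a maximum. No passage forces the analysis to start before follow-up ends, and routine care may supply the scans. So it does not follow that late patients will lack a reference, only that they lack it if the dates hold. The conflict between those dates and the 201 analysed still stands.

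The loss of power is moderate, and at 61 negatives the fixed-n figure is above plan. That reflects the steps of the exact test. The averaged figure is the fairer summary, and it falls.

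**Conclusion.** The point holds in this limited form and should be fixed. Three kinds of lesion have no sound reference label, and two of them can be labelled completely treated on their state after retreatment. If the expected dates hold, about 17 to 20 of the 201 patients, including about 6 to 7 of the 67 expected negatives, would have no 6-month reference in the analysis. Averaged specificity power would then fall from 82.7% to about 77-78%.

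The counts assume even accrual. They are upper figures, because some late patients could be labelled by (a) or (b). The power figures use the one-sided exact test of 7.2.1, without the multiplicity adjustment named in 7.2.

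A reader might go further and infer from Step 4 that the specificity result is likely to fail. The documents do not support that: they give no rate of unconfirmed retreatment or of clear explants after retreatment. The fall from 84.9% to 61.6% shows only how little mislabelling the design tolerates.

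**What to change.** 1. **3.1:** set the final analysis after the last patient's 6-month CE-MRI/CT and both read rounds. For a last TACE in December 2020, that means a scan in June 2021 and second reads in July 2021 at the earliest. Alternatively, close the analysed accrual correspondingly earlier and restate the analysed N and power in 7.2.1.
2. **Synopsis, 6.5 and 7.2:** state that reference status is the lesion's state after the index TACE and before any further locoregional treatment. Explants or scans obtained after retreatment, negative or positive, do not by themselves set that status.
3. **Lesions retreated for CT/MR enhancement without angiography:** do not let them default to negative. Fix their primary label before the CEUS reads are unmasked, and report results with them counted as positive and with them excluded. Making them positive outright would drop the angiographic confirmation that tier (b) asks for, so both results are needed.
4. **Lesions with no usable reference:** do not default them to negative. Report their number and CEUS results, leave them out of the primary 2 × 2 tables, and add analyses that count them all as positive and all as negative. Leaving them out can cause partial-verification bias, and the two extreme analyses bound it.

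The cost is wording, a date change, a little more analysis, and results about 6 to 8 months later (or fewer analysed patients if accrual closes early). No new procedures are needed.
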